LOD	Limit of detection
LS	Least squares
MedDRA	Medical dictionary for regulatory activities
MITT	Modified Intent-to-Treat
PCR	Polymerase chain reaction
PK	Pharmacokinetic(s)
SAE	Serious adverse event
SAP	Statistical analysis plan
SE	Standard error
SSRC	Sponsor study review committee
TEAE	Treatment-emergent adverse event
ULN	Upper limit of normal
WHO	World Health Organization

1 INTRODUCTION

The purpose of this Statistical Analysis Plan (SAP) is to provide a description of the statistical methods to be implemented for the analysis of data from the study with protocol number MAU868-201. The SAP will be finalized prior to database lock. Any deviations from the SAP after database lock will be documented in the final Clinical Study Report (CSR).

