10 STATISTICS

A detailed analysis plan will be described in a separate Statistical Analysis Plan (SAP). The SAP will supersede the protocol in the event of any differences between the 2 documents in the plans for data analysis, and the protocol will be amended if appropriate. The SAP will be included as an appendix in the clinical study report for this protocol.

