8 INTERIM ANALYSIS

8.1 First Interim Analysis

Following completion of the 12-week treatment period of Cohort 1, unblinded safety and tolerability data (adverse events, clinical laboratories, vitals/physical exams and ECGs), efficacy data (BKV viral load in the plasma) and PK (MAU868 plasma levels) will be provided in the form of individual subject case data packages and reviewed by the SSRC. The treatment assignment in Cohort 1 will be unblinded; however, these data will not include associated subject or site identifiers. The objectives of this interim analysis/this data review are to evaluate whether four doses MAU868 1350 mg IV administered every 28 days for a total of 4 doses demonstrate:

- safety and tolerability signals compared to placebo
- a decrease in BK plasma viral load compared to placebo
- predicted MAU868 plasma levels

The conclusions from this first interim analysis will be used by the Sponsor to evaluate the safety and efficacy of MAU868 early-on in this first-in-patient study. Unless a significant safety issue related to administration of MAU868 has been identified, the conclusions will have no impact on Cohort 2 or the study's design.

For the first interim analysis, unblinded programmed patient profiles will be provided.

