8.2 Second Interim Analysis

Following completion of the 12-week treatment periods for Cohorts 1 and 2, cumulative unblinded programmed data from both cohorts will be reviewed for safety and tolerability (adverse events, clinical laboratories, vitals/physical exams and ECGs), efficacy (BKV viral load in the plasma) and PK (MAU868 plasma levels). The objectives of this second interim analysis are to evaluate whether four doses MAU868 1350 mg IV administered every 28 days for a total of 4 doses or MAU868 6750 mg IV administered as a first dose followed by 3 more doses of MAU868 1350 mg IV administered every 28 days demonstrate:

- safety and tolerability signals compared to placebo
- a decrease in viral load compared to placebo

- predicted MAU868 plasma levels

Based on the SSRC's assessment of safety and tolerability and the sponsor assessment of the safety and tolerability, efficacy and PK conclusions for Cohorts 1 and 2, the dosing regimen for Cohort 3 may be adjusted in dosage and/or duration; however, the dosage and duration for Cohort 3 will not exceed the dose already specified in the protocol. Cohort 3 will not be opened for screening and enrollment this evaluation has been completed.

For the second interim analysis, cumulative unblinded programmed patient profiles will be provided. In addition, the programmed statistical tables and listings for Cohorts 1 and 2 will be presented.

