8.2.2 Cohorts 1 & 2: Response to Study Treatment

The following efficacy endpoints are included in the second interim analysis and will be assessed by the SSRC for subjects in Cohorts 1 and 2. The analysis will be performed based on the MITT Population and will be repeated on the ITT Population.

- Time (weeks) to decrease of BKV plasma viral load by 1 log;
- Time (weeks) to first decrease of BKV plasma viral load to <LLOQ ;
- Proportion of subjects with ≥ 1 log decrease of BKV plasma viral load by 1 week, 2 weeks, 4 weeks, 8 weeks, and 12 weeks;
- Proportion of subjects with decrease of BKV plasma viral load to <LLOQ by 1 week, 2 weeks, 4 weeks, 8 weeks, and 12 weeks;
- Rate of decrease in BKV plasma viral load by 1 week, 2 weeks, 4 weeks, 8 weeks, and 12 weeks;
- Change in eGFR from baseline to week 12;
- Proportion of subjects with BKV nephropathy through week 12;
- Proportion of subjects with graft failure through week 12;
- Proportion of subjects with acute rejection through week 12;
- Proportion of subjects who have died through week 12.

In the efficacy analyses, pairwise contrasts comparing each of the two active groups to the combined placebo group will be tested. The treatment groups will be 3 levels (i.e. Cohort 1 active group, Cohort 2 active group and combined placebo group). The analyses will be conducted using two sided tests at the alpha=0.05 level of significance, with no adjustment for multiplicity.

The efficacy endpoints above for the second interim analysis will be summarized and analyzed in the same manner as described in Section 7.5.1 with the exception that Cohort 3 subjects will not be included in the interim analysis.

8.2.3 Pharmacokinetics Cohort 1 and 2

MAU868 serum concentrations through Week 16 will be evaluated by the SSRC for both Cohorts 1 and 2. The pharmacokinetic analyses will be performed by another vendor and described in a standalone PK analysis plan.

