9 CHANGES FROM PROTOCOL-SPECIFIED STATISTICAL ANALYSES

The following changes are made in the SAP compared to the description in the protocol as clarification:

- Changed the MITT Population definition ‘subjects who received at least 1 dose of study drug and has at least 1 post-baseline plasma BK viral load result available’ to be ‘subjects who had the disease under study (had renal transplant within the year with a graft that is currently functioning and have met the BK viremia protocol entry criteria [baseline BK PCR plasma viral load test result ≥ 103 based on central laboratory data]), received at least 1 dose of study drug and have at least 1 post-baseline plasma BK viral load result available.’.
- Added the following efficacy endpoints:
 - Time (weeks) to first decrease of BKV plasma viral load to <LOD;
 - Proportion of subjects with decrease BKV plasma viral load to <LOD by 1 week, 2 weeks, 4 weeks, 8 weeks, 12 weeks, 16 weeks and 36 weeks.
- Added ‘Week 16’ in the following efficacy endpoints:
 - Proportion of subjects with ≥ 1 log decrease of BKV plasma viral load by 1 week, 2 weeks, 4 weeks, 8 weeks, 12 weeks and 36 weeks;
 - Proportion of subjects with decrease BKV plasma viral load to <LLOQ by 1 week, 2 weeks, 4 weeks, 8 weeks, 12 weeks and 36 weeks;
 - Proportion of subjects with decrease BKV plasma viral load to <LOD by 1 week, 2 weeks, 4 weeks, 8 weeks, 12 weeks and 36 weeks;
 - Rate of decrease in BKV plasma viral load over time by 1 week, 2 weeks, 4 weeks, 8 weeks, 12 weeks and 36 weeks;
 - Change in eGFR from baseline to week 12 and from baseline to week 36;
- Added ‘Week 12, Week 16, and Week 36’ in the following efficacy endpoints:
 - Proportion of subjects with BKV nephropathy;
 - Proportion of subjects with graft failure during the study;
 - Proportion of subjects with acute rejection during the study; and
 - Mortality rate during the study.
- Added ‘rate of decrease in BKV plasma and urine viral load over time by 1 week, 2 weeks, 4 weeks, 8 weeks, 12 weeks, 16 weeks and 36 weeks’ in the exploratory endpoints.

- Added presence of genotype and genotypic resistance and association with outcome in the exploratory endpoints, which will be described in a separate report.

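### The SAP may be finalised as late as database lock, after two unblinded efficacy reviews, so the plan permits late changes to the efficacy population and time points

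*SAP*

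**What the plan says.** - **Deadline.** SAP Section 1: "The SAP will be finalized prior to database lock". Only deviations after lock must be documented in the study report.
- **Precedence.** Protocol Section 10: "The SAP will supersede the protocol in the event of any differences between the 2 documents in the plans for data analysis". The protocol is amended only where that is judged appropriate.
- **First interim (SAP 8.1), after Cohort 1's treatment period.** "The treatment assignment in Cohort 1 will be unblinded; however, these data will not include associated subject or site identifiers". The data include plasma viral load, and "For the first interim analysis, unblinded programmed patient profiles will be provided".
- **Second interim (SAP 8.2 and 8.2.2), after Cohorts 1 and 2.** Unblinded profiles are supplied again. "In addition, the programmed statistical tables and listings for Cohorts 1 and 2 will be presented". For efficacy, "pairwise contrasts comparing each of the two active groups to the combined placebo group will be tested", at two-sided 0.05 on MITT and ITT. Cohort 3 cannot open until this review is complete (SAP Section 5).
- **Who reviews.** The Sponsor Study Review Committee (SSRC) consists of a sponsor medical representative, the Medical Monitor and a site Principal Investigator (SAP Section 5). SAP 8.2 also refers to the sponsor's own assessment of efficacy. Protocol 4.3 and SAP 2.2.2 describe the study as sponsor-blinded.
- **Departures from the protocol.** SAP Section 9 introduces its list thus: "The following changes are made in the SAP compared to the description in the protocol as clarification". The list includes a new MITT definition and an added Week 16.
- **Nephropathy.** SAP 7.5.1.9 removes certain biopsy-proven BKV nephropathy cases from the summary on the SSRC's opinion, with documentation.

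**The concern.** If a population or time point is settled by people who have seen results by arm, the reported effect and its p-value no longer have their nominal meaning. With 8 subjects per active group, one subject is 12.5% of the group, so a baseline filter that removes one or two can move an estimate visibly. The protocol makes the MITT analysis the primary efficacy analysis (Section 10.3), and the study exists to decide whether MAU868 deserves further development (Section 1.5). A reader of the final report needs to know which analysis choices were made before treatment-labelled data were available. The plan contains no rule that would guarantee this.

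**Working it through.** **1. The plan's own figures.** Three cohorts of 12 give 3 × 12 = 36 subjects, with 3 × 8 = 24 on MAU868 and 3 × 4 = 12 on placebo. This reproduces SAP Section 3. No power or effect size is stated.

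**2. Order of events.** The first interim unblinds 12/36 = 33% of planned subjects. The second brings this to 24/36 = 67% (16 of 24 active, 8 of 12 placebo). Cohort 3 opens only afterwards, so both reviews precede the final database lock. Section 1 pairs the lock with deviations reported in the final study report, so the final lock is the natural reading. The SAP may therefore still be edited after both reviews.

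**3. The population change.**

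| | Protocol 10.3 | SAP 7.2.2 |
|---|---|---|
| At least 1 dose | yes | yes |
| At least 1 post-baseline plasma result | yes | yes |
| Transplant within the year, functioning graft | not required | required |
| Central baseline load at least 10^3 | not required | required |

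Protocol 3.2.1 lets subjects qualify on a local or central result up to 10 days before randomisation. SAP 7.1.3 takes baseline as the last value before the first dose. A subject who was validly randomised and treated can therefore fall out of the SAP's MITT. The documents do not say how many might.

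**4. The other changes.** Week 16 is one more reported time point; the protocol's time points stay. Section 9 lists the limit-of-detection endpoints as added, but Protocol 10.5.1 already has time to, and proportion below, the lower limit of detection. The protocol synopsis and Section 2.3 use the limit of quantification instead. Reporting both settles an inconsistency within the protocol.

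**5. Nephropathy exclusions.** SAP 7.5.1.9 gives conditions: no pre-study biopsy, stable or improving creatinine, and improving plasma viral load. The final decision is the SSRC's opinion. That committee will have seen unblinded data, and the text does not require this decision to be blind.

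**6. Size, as an illustration only.** Assume no treatment effect, one endpoint, and a filter that drops each subject at random with probability 10% or 25%. At the second interim (8 active, 8 placebo) the population with the smaller p-value is chosen; the final test uses 8 active and 12 placebo. The drop rates and the selection rule are assumptions.

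| Test | Population fixed in advance | Population chosen at second interim |
|---|---|---|
| t test, 10% dropped | 4.8% | 6.1% |
| t test, 25% dropped | 5.0% | 7.4% |
| Fisher's exact test, 10 to 25% dropped | 1.1 to 2.3% | 2.2 to 3.5% |

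The t-test rows use 20,000 simulated trials per setting (Monte Carlo standard error about √(0.05 × 0.95 / 20,000) = 0.15 percentage points). The fixed Fisher figures are exact, for event rates of 10 to 70%. The chosen-population Fisher figures use 40,000 simulated trials per setting, for event rates of 20 to 70%. Fisher's test is conservative at these sizes, so selection raises its error rate but leaves it under 5%.

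**The case against.** The strongest reply is that nothing shows a data-driven choice, and much in the text points the other way. Section 8 describes both interims in the future tense. Section 8.2.2 runs the second interim on the MITT and lists no limit-of-detection endpoint and no efficacy time point after Week 12. The baseline filter uses a pre-dose value and echoes an entry threshold. Section 9 itemises the changes openly. Efficacy is repeated on ITT, which contains the protocol's MITT. All Cohort 3 data arise after the second interim. Interim data carry no subject or site identifiers, and access controls may sit in the SSRC Charter, which is not available here. Safety is the primary objective, and efficacy is unpowered proof of concept.

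Most of this stands and limits the weight of the point. It does not close the gap. The ITT repeat guards only partly against the population change, because it is not the protocol's MITT and does not bear on time points. Future tense describes this text; it does not bind a later revision. The statement that the first interim will not affect Cohort 2 or the design does not bar SAP edits.

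A reader might infer three stronger things, and the documents support none of them:

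- **That the Section 9 changes followed the unblinding.** The text does not show this. The missing version date cannot be held against the plan, because front matter was removed from the copy reviewed.
- **That the limit-of-detection endpoints are a new choice.** They are in Protocol 10.5.1.
- **That two populations, two assay limits, and with or without Week 16 make 2 × 2 × 2 = 8 tries, with a 16 to 34% chance of a false positive.** The upper figure, 1 − 0.95^8 = 34%, needs independence. That is impossible: below 26 copies/mL is a subset of below 39, and the SAP's MITT is a subset of the protocol's. Both limits are reported, and Week 16 replaces nothing. Such a figure measures the openly unadjusted multiplicity, which remains whenever the SAP is signed.

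**Conclusion.** The point holds as a statement about what the plan permits. The sponsor may revise the efficacy population and time points after its representative has seen results by arm for 24 of 36 planned subjects, and neither document describes a separation between that knowledge and SAP editing. The narrowed MITT matters most, the unblinded nephropathy exclusions come next, and Week 16 is minor. The size of any bias cannot be fixed from the documents. Under the assumptions shown, choosing the population alone takes a nominal 5% t test to about 6 to 7%, and leaves Fisher's exact test below 5%. This is a cheap improvement. It gives no ground for discounting the trial's results.

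**What to change.** 1. In SAP Section 1, state that the SAP, including the MITT definition, endpoints and time points, is finalised and signed before the first unblinded interim.
2. Have later changes made by staff without access to interim data, dated, and marked as post-interim in Section 9.
3. Report the protocol-defined MITT beside the SAP's MITT.
4. In SAP 7.5.1.9, have the exclusions from the nephropathy summary decided by reviewers blind to treatment. The SAP already commits to reporting all such biopsies in the study report, and that should stay.
5. If an interim has already taken place, state when each Section 9 change was made relative to it and who was unblinded, and label later changes post hoc.

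The cost is wording, an earlier sign-off, one extra set of efficacy tables and blinded reviewers for a few cases. No patients or visits are added. The downside is less freedom to revise late: a change to Cohort 3's regimen after the second interim, which the plan allows, would need a marked SAP amendment.

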2 STUDY OVERVIEW

2.1 Study Objectives

2.1.1 *Primary Objective*

The primary objective of this study is to assess the safety and tolerability of MAU868.

2.1.2 *Secondary Objectives*

The secondary objectives of this study are to:

- Assess the impact of MAU868 on BK viremia and BK viremia related outcomes i.e., BK virus nephropathy, graft function and acute rejection among renal transplant recipients with BK viremia; and
- Assess the pharmacokinetics of MAU868.

2.2 Study Design

2.2.1 *Overview*

This is a randomized, placebo-controlled, double-blinded, proof-of-concept study in kidney transplant recipients. Up to 36 subjects with BK viremia will participate in 1 of 3 sequential cohorts. Each cohort will randomize approximately 12 subjects (8 MAU868 and 4 placebo).

The study will consist of a screening period, a 12-week treatment period and a 24-week follow up period.

Protocol-specific procedures should not be performed until the patient has consented to participation in the study. However, assessments and procedures performed as part of standard of care prior to informed consent, including determination of BK viral load in plasma may be used to qualify a patient for the study. Once qualifying BK viremia has been confirmed, subjects should be randomized as soon as possible and no more than 10 days after the sample documenting the viremia was collected.

During the treatment period, subjects will receive MAU868 or placebo approximately every 28 days (every 4 weeks) for 12 weeks (4 doses total). Urine and blood will be monitored for BKV DNA by polymerase chain reaction (PCR) weekly for the first 6 weeks after initiation of treatment. For the remainder of the treatment period, urine and blood must be collected for BKV DNA by PCR at least every other week. However, the Investigator may also request testing more frequently (i.e., weekly) than mandated by the protocol after the first 6 weeks of treatment and when clinically indicated. During the study, BKV DNA by PCR will be tested at the central laboratory. Pharmacokinetics (PK), viral resistance, and anti-drug antibodies (ADA) will also be monitored. Subjects should continue study drug until the last scheduled dose, regardless of changes in plasma

BK viral load, use of rescue therapy, and/or need for change in immunosuppressive regimen for any reason.

[figure not shown]
During the 24-week follow-up period, 3 follow-up visits will be scheduled. At each visit, urine and blood samples for BKV DNA and samples for PK will be collected. Investigators may collect samples for BKV DNA more often as clinically indicated. During the follow-up period, BKV DNA by PCR will be tested at the central laboratory.

Routine post-transplantation care is to be guided by the Investigator's discretion and site standard of care. This includes decisions to change the immunosuppressive regimen for a subject for any reason except for changes in immunosuppression in response to BK viremia. In order to treat BK viremia, prior to randomization, (i.e., prior to screening, during the screening period and at the Baseline Visit) Investigators are permitted to decrease or alter immunosuppressive therapy at their discretion and/or per standard of care at their site. However, in the first 4 weeks after randomization, Investigators should refrain from additional changes in immunosuppressive regimen in response to BKV unless the viral load has increased by >1 log and the Investigator determines that a change is in the best interest of the subject. Use of other antiviral agents including cidofovir and leflunomide as well as IVIG are not permitted during the first 4 weeks of therapy and are strongly discouraged thereafter.

Use of fluoroquinolones for reasons other than treatment of BKV is permitted.

Between screening and the last visit, subjects will attend a total of 14 planned visits. Unscheduled visits are permitted at the Investigator's discretion.

A schematic representing the study's design is included below.

2.2.2 Randomization and Blinding

Study participants will be randomly assigned to their treatments. Two participants will be assigned to receive treatment with MAU868 for each participant assigned to receive treatment with placebo (2:1 randomization). Randomization will occur via an Interactive Web Response System (IWRS). The Investigator or delegate will contact the IWRS after confirming that a potential study participant is eligible. The IWRS will assign a randomization number that will be used to link the subject to a treatment arm.

The randomization number is only used to identify which treatment study participants have been assigned to receive. The number assigned to a subject at screening remains the unique identifier for the subject throughout the study. The randomization numbers will be generated using procedures that ensure that treatment assignment is unbiased and concealed from the Sponsor, subjects, and Investigator staff.

This is a subject, Investigator, and Sponsor-blinded study. Subjects and Investigators will remain blinded to study treatment arm (MAU868 or placebo) throughout the study.

Drug product will be supplied in bulk, so an unblinded pharmacist, or appropriately designated study site staff who is independent of the study team, will be required in order to maintain the blind. This unblinded associate at the site will be notified by the IWRS that a subject is randomized and to which treatment arm, which will then enable and instruct them to prepare the study drug.

2.2.3 Breaking the Blind

Blinding is critical to the integrity of this clinical study. However, in the event of a medical emergency or pregnancy in an individual subject, in which knowledge of the investigational product is critical to the subject's management, the Investigator should contact the Medical Monitor to review the situation prior to breaking the blind.

Before breaking the blind of an individual subject's treatment, the Investigator should have determined that the information is necessary (i.e., that it will alter the subject's immediate management). In many cases, particularly when the emergency is clearly not investigational product related, the problem may be properly managed by assuming that the subject is receiving active product without the need for unblinding.

When the Investigator contacts the system to break a treatment code for a subject, he/she must provide the requested subject identifying information and confirm the necessity to break the treatment code for the subject. The Investigator will then receive details of the investigational drug treatment for the specified subject via the IWRS. The system will automatically inform the study monitor for the site and the Study Team that the code has been broken.

It is the Investigator's responsibility to ensure that there is a dependable procedure in place to allow access to the IWRS /code break at any time in case of emergency.

An assessment will be done by the appropriate site personnel and Sponsor after an emergency unblinding to assess whether or not study drug should be discontinued for a given subject.

In cases of accidental unblinding, contact the Medical Monitor and ensure every attempt to preserve the blind is made.

